7.6 Final visit (Visit 8)

- This visit will occur 14 (+2) days from the start of the second arm.
- Participants will return to the clinic and answer the post questionnaires for the study arm or will complete the study visit virtually via Zoom.
- The body weight of the participant will be documented.
 - *If the visit is conducted virtually, the participant will measure body weight at home and a verbal report of their weight will be acceptable.*
- Study staff will review any changes in the participant's medical history or medications to ensure continued eligibility and will document any adverse events that may have occurred since their last study visit.
 - Study staff will specifically ask participants if they had any infusion site or CGM sensor site reactions or other skin irritation during the arm and will document any reactions.
 - Any changes to medications or medical history and any adverse events that may have occurred since their last study visit will be documented.
- Study devices will be downloaded as applicable (CGM, glucometer, InPen, iLet).
 - *If the visit is done virtually, participants will ship study devices back to the site in the provided shipping materials.*
- All equipment will be collected.
- A study provider will review the last few hours of glucose trend data and insulin on board from the iLet and assist the participants in resuming their usual diabetes management.

7.7 General Study Policies for both Study Arms:

- Participants will keep their study issued Contour Next One glucometer easily accessible at all times. They will keep a glucometer, fast-acting carbohydrates, and a glucagon emergency kit easily accessible.
 - Participants will be encouraged to check their BG as often as they wish to confirm the accuracy of the Dexcom CGM and for safety, as well as to maintain adequate control of glycemia in the Usual Care arm. However, they should use the study provided glucose meter for all checks.
- Participants may not take hydroxyurea during all study arms due to potential interference with CGM sensing. Hydroxyurea is known to interfere with the accuracy of the Dexcom CGM.
- Participants are not allowed to exceed the maximum daily doses of acetaminophen from all sources during the study due to potential interference with the Dexcom G6 CGM.
 - Adult: 1 g every 6 hours, up to 4 g every 24 hours
 - Pediatric: 75 mg/kg/day in up to 5 doses, not to exceed 4000 mg/day
- Any medical advice needed by the participants during their participation, which is not directly related to BG control during the experiment, should be obtained by them in the usual manner with

their primary care physician, pulmonologist, or endocrinologist.

- If a participant develops an illness during the experiment, they can seek medical care as usual. As long as the participant is not hospitalized, the study can be continued. If the participant is unable to eat for a period exceeding one day, they must notify study staff so that the medical staff can assess the safety of continuing in the study.
 - If a participant requires hospitalization during the experiment, they will discontinue the experiment and their participation in that study arm will end. The data collected up to their admission will not be used for the primary glycemic analysis but will be used in safety analyses. The participant can restart the study arm 2 weeks after discharge, but no later than 4 weeks after discharge.
- If a participant has exacerbation requiring oral glucocorticoid therapy, they can continue with all study arms as long as they do not require hospital admission.
- Participants may participate in any activities that they wish, as long as they abide by the policies above.
- There are no restrictions of any kind on diet or exercise, although participants should attempt to maintain similar dietary habits and exercise habits during each arm of the study. The iLet bionic pancreas must be kept dry during exercise.
- Participants may choose to withdraw from the study at any time. If they withdraw from the study, they should contact a provider immediately. If they are wearing the bionic pancreas, a provider will help them transition to their own insulin regimen safely. If the participant wishes to discontinue use of the bionic pancreas but is willing to continue in the study, they will be asked to continue to wear the Dexcom G6 CGM for the entire study period and complete the study visits to facilitate full data collection and analysis by the intention to treat principle.
- Participants will be asked to report all hypoglycemia, carbohydrate interventions, any adverse events, time spent exercising, any unscheduled infusion set changes, alcohol use, and other questions through a daily email survey.

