1.2 Bionic Pancreas System

We have developed an autonomous, self-learning BP that requires only the participant's weight for initialization, then autonomously adapts to cope with the wide range of insulin requirements. This system has been studied in adults, adolescents, and pre-adolescents with type 1 diabetes (T1D), and as well as patients with insulin dependent type 2 diabetes (T2D) (30-36). The BP obviates the need for the patient to know their insulin requirements, and renders obsolete any need for patients or caregivers to know carbohydrate-to-insulin ratios, basal rates, or insulin correction factors. We propose utilizing this system for the management of CFRD.

The core technology is the insulin controller, which orchestrates all subcutaneous (SC) insulin dosing. At its centerpiece is a model-predictive control algorithm, which bases insulin doses on glucose data and insulin absorption and clearance kinetics. The bionic pancreas algorithm was the first to incorporate insulin pharmacokinetics (PK) into the algorithm by augmenting the insulin controller with a mathematical formulation for estimating the concentration of insulin in the blood and predicting its future concentration. It is essential to compensate for the slow absorption rate of SC insulin analogs (peak time in blood of 30–90 min, clearance in 4–8 hr), and to enable the algorithm to refrain from stacking and overdosing insulin. Furthermore, the MPC algorithm automatically adjusts its insulin-dosing aggressiveness continuously and in real-time to different insulin needs between individuals and variable needs within the same individual.

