Running in parallel with the MPC algorithm is an algorithm that automatically modulates basal insulin delivery over multiple time scales, and another algorithm that automatically adapts insulin doses in response to optional meal announcements. Unlike current insulin pumps, and all of the other insulin-only control algorithms of which we are aware, the adaptive basal insulin algorithm obviates the need for the user to set, or even know, his or her basal-rate profile. Instead, it is capable of automatically adapting to, and compensating for, changes in an individual's basal insulin need, such as might occur over a period of hours, days, or weeks (e.g. circadian hormonal fluctuations, intercurrent illness, physical activity, or emotional state) or as might occur over a period of months or years due to developmental changes (e.g. hormonal changes that occur during puberty or menopause). The adaptive meal dose controller obviates the need for the user to set, or even know, his or her carbohydrate-to-insulin ratios, as it makes automatic adjustments based on dosing history for similar meal announcements made on previous days, and customizes the dose for each individual and for time of day. The bihormonal configuration of the BP also includes a proportional-derivative algorithm governing SC micro-doses of glucagon to help prevent impending hypoglycemia. Glucagon dosing is based on the glucose level and rate of descent. It could occur preemptively even if glucose is above range and it includes a feedback term to account for the pending effects of recent glucagon doses.

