- If the participant is a transplant recipient taking steroids and/or calcineurin inhibitors, they will be instructed to notify the study team of any dose changes while they are wearing the iLet bionic pancreas. If a change occurs, study staff will review their CGM Clarity data daily for three days after the change to make sure the iLet has adapted well. Based on this review of CGM data, a change in glucose target may be indicated.

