11.2.2.2 Reporting guidelines

Any serious or unexpected but possibly related adverse events will be communicated to the PI as soon as possible and within 24 hours of the time they are detected. Adverse events and unanticipated problems will be reported to the Partners IRB, the DSMB and Beta Bionics. Reports of adverse events will be made to the FDA in compliance with the terms of IDE.

12. Participant Compensation

Financial compensation will be provided to all participants who complete the screening visit. Participants will be paid \$25 for completing the screening visit whether or not they are eligible to participate in the study.

Study participants will be compensated \$75 for completing each study visit (study start, crossover, and final). The total compensation for a participant who completes the screening visit and scheduled study visits (study start, crossover, and final) would be \$250.

13. References

1. Registry CFFP. Annual Data Report Bethesda, Maryland: Cystic Fibrosis Foundation; 2018.

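### The staff check on glucose control after a steroid change on the iLet covers transplant recipients only, although other participants may also continue through an oral glucocorticoid course

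*Combined protocol and SAP*

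**What the plan says.** Section 7.7 (general policies for both arms) permits continuation through a steroid-treated exacerbation: "If a participant has exacerbation requiring oral glucocorticoid therapy, they can continue with all study arms", short of hospital admission. The bullet gives no instruction to tell staff. The same section does attach one to another illness event: "If the participant is unable to eat for a period exceeding one day, they must notify study staff". Section 11.2.1 separately allows removal for an illness that precludes safe participation, so continuation is permitted but not guaranteed.

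Section 7.7.2 (iLet arm) deals with steroid changes in one subgroup. "If the participant is a transplant recipient taking steroids and/or calcineurin inhibitors, they will be instructed to notify the study team" of dose changes while on the device. After that, "study staff will review their CGM Clarity data daily for three days after the change to make sure the iLet has adapted well", and a target change may follow. Section 4.2 already requires this subgroup's steroid and/or calcineurin inhibitor doses to have been stable for a month, with no significant change expected.

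Section 1.1 says that people with CF in general often receive glucocorticoid courses and that these can cause hyperglycemia. It does not limit this to transplant recipients.

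**The concern.** The protocol expects two kinds of steroid change on the iLet and treats them differently. The group screened for stable doses gets a staff check. A participant who begins a new course for an exacerbation, which Section 7.7 expressly anticipates, does not.

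The stated purpose of the transplant check is to confirm that the device has adapted. In that subgroup, then, the protocol does not rely on adaptation alone after a steroid change. Section 6 trains participants not to alter the permanent target without the study team, so staff must know of a course before they can consider a target change because of it. Section 7.7 also sends participants to their usual physicians for care not directly related to glucose control, so the course may be prescribed outside the study.

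At stake is how soon staff look at glucose control after a steroid change. The validity of the comparison is not in question.

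**Working it through.** The plan gives no figure on this point. The main check is to list every safeguard that could apply to a non-transplant participant on the iLet and ask what sets it off.

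| Safeguard | Section | Set off by |
|---|---|---|
| Device alarms | 7.7.2 | Glucose level or rate of fall |
| Ketone check | 7.7.2, 7.7.4 | CGM above 300 mg/dl for 90 minutes, above 400 once, or ketoacidosis symptoms |
| Contact staff | 7.7.2 | Hyperglycemia lasting more than 2 hours |
| Fingerstick check | Appendix C | Suspected set failure, CGM above 300 mg/dl for 90 minutes, or being sick |
| Notify staff | 7.7 | Unable to eat for more than a day |
| Daily email survey | 7.7, 11.1 | Every day; asks about adverse events |
| Investigator review of adverse events | 11.2.2.1 | An adverse event; no deadline given |
| Report to the PI within 24 hours | 11.2.2.2 | Serious events, or unexpected and possibly related ones |
| Check-in calls | 7.3, 7.5 | Days 2 and 5 of the arm, each ±1 |
| Review of medication changes | 7.4, 7.6 | The visit that ends the arm |
| Provider on call | 7.7.7 | The participant's own call |

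No row is set off by a steroid change. The nearest is the survey: "Participants will be asked to report all hypoglycemia, carbohydrate interventions, any adverse events" each day. An exacerbation needing oral steroids fits the adverse event definition in Section 11.2.2.1, so it should be reported. What is missing is the next step. No section requires same-day reading of the survey or a CGM review after such a report. The fast route covers this: "Any serious or unexpected but possibly related adverse events will be communicated to the PI as soon as possible and within 24 hours". An exacerbation managed outside hospital would often be neither serious nor unexpected.

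**Calendar gap.** The last call falls on day 4–6 and the visit ending the arm on day 14–16. The gap is 14 − 6 = 8 to 16 − 4 = 12 days. A course starting at a uniformly random time in it waits 8/2 = 4 to 12/2 = 6 days on average for the next scheduled contact, and that contact ends the arm. The optional sensor reminder at 10 days applies to usual care only. This describes the schedule and is not a risk estimate, because the survey or a glucose trigger may bring staff in sooner.

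**Effect on the primary analysis.** Section 8.3 gives time in range of 50 ± 18% and 70 ± 12% with correlation 0.3.
- SD of the paired difference = √(18² + 12² − 2 × 0.3 × 18 × 12) = √338.4 = 18.4. This reproduces the plan's nine participants (power 81.4% at 9, 75.1% at 8).
- SE at 20 participants = 18.4/√20 = 4.11.
- Assume that a course lowers time in range by 15–30 points on 5–7 of the 12 analysed days. That participant's arm mean falls by 5 × 15/12 = 6.25 to 7 × 30/12 = 17.5 points.
- The group mean moves by 6.25/20 = 0.31 to 17.5/20 = 0.88 points per affected participant, or 0.08 to 0.21 SE.

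**Workload of the fix.** Assume that 5–10% of participants have a course on the iLet, and take all 30 as non-transplant (an upper bound). The low end, with one reviewed change each, is 30 × 0.05 × 3 = 4.5 reviews. The high end, with a start and a stop each, is 30 × 0.10 × 6 = 18. A stepped taper would add more.

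**Extra attention in an open-label arm.** Assume that the reviews raise time in range by up to 5 points on 7 of 12 days in 2 of 20 participants. The mean then moves by 5 × 7/12 × 2/20 = 0.29 points, or 0.07 SE.

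**The case against.** The device is designed for this situation. Its algorithm "automatically adjusts its insulin-dosing aggressiveness continuously and in real-time", and Section 1.2 says it compensates for changes in "basal insulin need, such as might occur over a period of hours, days, or weeks (e.g. circadian hormonal fluctuations, intercurrent illness" among them). The transplant rule also has a visible reason: it reads as the on-study counterpart of the dose-stability condition in Section 4.2, and it covers calcineurin inhibitors as well. It need not mean that the sponsor thought the same check worthwhile for every short course. The rule sending hyperglycemia of more than 2 hours to staff acts on the harm itself, whatever its cause. The available lever is small: Section 6 allows one 10 mg/dl step either way from the default target, and a permanent change only when important for safety. The fix would also depend on self-report, as the survey does.

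Most of this stands, and it limits the point to an improvement. A reader might infer that staff would not learn of the exacerbation, or that these participants are unprotected. The documents do not support that: the daily adverse event report, the illness-triggered fingerstick check and the glucose-triggered contact all apply. A reader might also see a contradiction between Sections 7.7 and 7.7.2. There is none, since a narrower rule for one subgroup is coherent. What remains is that no safeguard connects a steroid change to a look at the CGM data.

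**Conclusion.** The point holds as a modest gap in safety oversight. Participants without a transplant may continue on the iLet through an oral glucocorticoid course, and nothing directs staff to review their glucose data because of it.

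The documents do not give the frequency of such courses, the harm that earlier review would avoid or the glycemic effect of a target change, so no size is claimed for any of these. The workload estimate rests on the assumed 5–10% course rate. A reader might infer that steroid courses threaten the primary result. They do not: under the assumed loss, one affected participant shifts the mean by less than 1 point against a planned 20.

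Section 1.1 speaks only of hyperglycemia. Covering the end of a course assumes that insulin need may change then too, although the existing transplant rule already applies to any dose change.

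**What to change.** In Section 7.7.2, keep transplant recipients as now and add: *and any participant who starts, changes or stops oral glucocorticoids while wearing the iLet*. Apply the same notification, three days of daily CGM review, and consideration of the target within the Section 6 settings (110, 120 or 130 mg/dl). Section 11.1 makes cloud streaming conditional on use of the Clarity app. Where it is not used, do the review by phone from the glucose history on the iLet display. Cross-reference the rule in the Section 7.7 steroid bullet, next to the existing duty to notify when unable to eat.

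The cost is one sentence, one cross-reference and a few extra daily reviews by existing staff. The other downside is slightly more attention in the open-label iLet arm, which is negligible under the inputs above. Eligibility to continue, the dosing algorithm and the intention-to-treat analysis do not change.

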7.7.1 Usual Care Arm

- In the Usual Care arm, participants will continue to manage their own BG according to their usual practice. If they routinely use a CGM, they will be encouraged to continue to use it during the Usual Care period. They will be asked not to modify their insulin regimen without consulting their own endocrinologist.
- If a participant does not use the Dexcom G6 as part of their usual care, they will be given blinded Dexcom G6 Pro CGM sensors and transmitters and instructed to change it every 10 days during the usual care arm. If they do use the Dexcom G6 they will be asked to use it throughout the entire study period.
- Participants will be trained to respond to hypoglycemia and hyperglycemia according to their usual practice and best practice recommendations.
- If a participant uses multiple daily injections as part of their usual care, they will be provided with an InPen and taught how to use it.

7.7.2 Bionic Pancreas Study Arm

- Participants will keep their bionic pancreas charged, which will require charging with the study provided charger at least once per day.
- Participants will keep their study issued Precision Xtra ketone meter, extra infusion sets and insulin vials and syringes or insulin pens easily accessible at all times.
 - Participants will be required to check their ketone levels whenever their CGM has been above 300 mg/dl for 90 minutes and to notify study staff if the result is ≥ 0.6 mmol/l.

- During the experiment, the iLet bionic pancreas will be worn by the participant at all times to ensure good radio-frequency signal reception.
 - The bionic pancreas is not waterproof and therefore must be removed for water activities, including showering. Participants are urged to take appropriate precautions when they are disconnected from the bionic pancreas, including frequent BG checks and having carbohydrate readily available.
 - The Dexcom CGM transmitter is water resistant and can be left on for bathing and swimming.
 - Participants may not remove the iLet bionic pancreas for more than 1 hour at a time (e.g. for bathing) and may not remove it for more than 2 hours total in any 24-hour period.
- Participants will be asked to change their infusion set and cartridge every 3 days.
 - Participants will be taught to replace their infusion set if there is any doubt that it may not be working. They will be taught how to recognize potential infusion site failures.
 - Participants will be taught to replace their infusion set if their ketones are ≥ 0.6 mmol/l. More details pertaining to hyperglycemia management can be found in Appendix C.
- Participants will receive alerts if Dexcom CGM Bluetooth connection is interrupted for more than 2 hours.
 - If a Dexcom CGM sensor fails during the course of an experiment, the iLet will provide basal insulin based on past requirements and will allow announcement of meals and entry of fingerstick BG measurements, which will be treated by the algorithm in the same way as Dexcom CGM data and may result in administration of insulin or temporary suspension of insulin delivery. The Dexcom CGM sensor will be replaced as soon as possible and normal bionic pancreas control will resume when the new sensor is online.
- If there is a complete failure of bionic pancreas operation and it is anticipated that restarting it will take more than an hour, participants may take over their own BG control using their own insulin pump or with insulin injections until the bionic pancreas can be brought back online with the help of study staff.
 - If necessary, a staff member will meet the participant to assist with troubleshooting. This meeting may be delayed until morning if the problem occurs overnight - in this case, the participant will use their own pump until a meeting is possible.
 - If necessary, the bionic pancreas device may be replaced. If the failure occurs at night, every effort should be made to correct the problem as soon as possible, which should almost always be possible within 12 hours.
- Participants will be asked to announce the three major meals of the day, but not snacks, to the iLet bionic pancreas. The meal announcement will consist of choosing the type of meal (breakfast, lunch, dinner) and the size of the meal relative to typical meals for that participant (Usual for me, more than or less than usual).
- The iLet bionic pancreas will generate the following CGM glucose related alarms to the participant:
 - Urgent Low Glucose: ≤ 55 mg/dl
 - Low Glucose: ≤ 70 mg/dl
 - Fall Rate Alert: CGMG < 100 mg/dl and CGM trend is dropping more than 2 mg/dl/min
 - High Glucose: ≥ 300 mg/dl for 90 minutes
- Participants will be trained in recognizing and responding to all of these alarms.
- Participants will be trained on troubleshooting for various scenarios that could lead to a low glucose alarms. For instance, a threshold alarm could be due to true hypoglycemia, poor Dexcom CGM calibration, or a compression artifact at the site of the sensor.
 - The first step for all low glucose-related alarms will be to perform a fingerstick BG measurement.
 - If the BG measurement is not consistent with the CGM glucose, the participant will

assess the possibility of a compression artifact (they will be trained in the causes and recognition of these events). If a compression artifact is suspected, they will take steps to relieve the pressure on the transmitter. If compression is not suspected, they will calibrate the Dexcom CGM as long as there has been no food or carbohydrate intake in the last 30 minutes. If a calibration is delayed for this reason, it will be performed at the next opportunity if still necessary.

- If the BG measurement is consistent with a low glucose: the participant will treat hypoglycemia with carbohydrates. Participants will be instructed to consider using less carbohydrate to treat or prevent hypoglycemia, since due to insulin suspension 5-10 grams is often sufficient and is less likely to lead to hyperglycemia.
- Participants will be trained on troubleshooting for various scenarios that could lead to hyperglycemia. For instance, hyperglycemia could be due to true hyperglycemia or poor Dexcom CGM calibration.
 - The first step in responding to hyperglycemia according to the CGM will be to perform fingerstick BG and ketone measurements.
 - If the BG measurement is not consistent with the CGM glucose: the participant will calibrate the Dexcom CGM as long as there has been no carbohydrate intake in the last 30 minutes and there is no steep rise or fall in glucose (>2 mg/dl/min). If a calibration is delayed for this reason, it will be performed at the next opportunity if it is still necessary. The participant will be taught to continue to monitor CGM and BG measurements to confirm accuracy and normoglycemia.
 - If the BG measurement is consistent with the CGM glucose:
 - Participants will be asked to investigate their insulin infusion set and consider replacing it, check for any occlusions along the fluid path, and check to make sure that the cartridge is not empty.
 - Study staff will recommend the participant continue to monitor their BG until it returns to normoglycemia, and to contact study staff with any questions or concerns.
 - If ketones ≥ 0.6 mmol/L are present:
 - Participants will be advised to change their pump infusion set and will be reminded that the BP should dose insulin accordingly.
 - Study staff will recommend the participant continue to monitor their ketone levels and BG every 60 minutes until ketones return to < 0.6 mmol/L and BG is < 180 mg/dl, and to contact study staff with any questions.
 - If participants experience persistent hyperglycemia lasting more than 2 hours, they will be instructed to contact study staff for consideration of infusion set replacement and/or correction insulin according to the above protocol.
- If the participant is a transplant recipient taking steroids and/or calcineurin inhibitors, they will be instructed to notify the study team of any dose changes while they are wearing the iLet bionic pancreas. If a change occurs, study staff will review their CGM Clarity data daily for three days after the change to make sure the iLet has adapted well. Based on this review of CGM data, a change in glucose target may be indicated.

